5.3.3 Sensitivity analysis

No sensitivity analysis is planned for this study.

5.3.4 Supplementary analyses

No supplementary analysis is planned for this study.

5.4 Secondary Endpoint(s) Analysis

5.4.1 Key/Confirmatory secondary endpoint(s)

PK endpoints

- Maximum plasma concentration (C_{max})
- Time to maximum plasma concentration (t_{max})
- Area under the concentration-time curve from 0 to time t ($AUC_{(0-t)}$)

PD endpoints:

- Baseline-corrected area under the Total IgG-time curve
- Maximum decrease in total plasma IgG (R_{min})
- Time to minimum IgG level (t_{min})
- Total IgG

5.4.1.1 Definition of endpoint(s)

Pharmacokinetics will be determined by non-compartmental analysis in Phoenix WinNonlin (Certara, USA) using the PK Per Protocol Set.

For calculation of the plasma PK parameters of rozanolixizumab, the actual sampling time points along with the actual dose administered and duration of administration will be used in order to evaluate the PK parameters.

Venous blood samples will be collected at protocol specified time points for the measurement of Total IgG.

5.4.1.2 Main analytical approach

PK analyses

All PK summaries will be done using PK-PPS and displayed by method of administration (see [section 5.1.1.3](#)). The plasma concentration-time profiles and PK parameters of rozanolixizumab (C_{max} , AUC, and T_{max}) will be summarized by method, dose and body weight for rozanolixizumab treated patients using descriptive statistics (number of available observations, arithmetic mean, standard deviation, the geometric mean, the coefficient of variation of the geometric mean, median, minimum, and maximum). For t_{max} , only median, minimum and maximum will be reported. Values below LLOQ will be reported with a clear sign indicating that they were below the LLOQ. Descriptive statistics of concentrations will be calculated if at least two-thirds of the individual data points are quantifiable (\geq LLOQ).

Individual and spaghetti concentration time profiles will be displayed graphically on a linear-linear scale and semi-logarithmic scale. Geometric mean plasma concentrations-time curves including 95% CI will be displayed.

The comparability of dose-adjusted PK parameters (C_{max}/D and $AUC_{(0-t)}/D$) between the methods (MP and the syringe driver) will be assessed within an analysis of variance (ANOVA) model with method (MP vs syringe driver) as a main effect, with no additional covariates. The log-transformed PK parameters will be used in the ANOVA model. The model structure to be used is therefore

$$\log(\text{Parameter}) \sim \text{Method of Administration}$$

This model structure has been chosen to reflect the intended dosing scheme of fixed dosing (e.g., of ██████) applied to adults >35 kg irrespective of weight. This will thus allow us to draw conclusions about the presence or absence of effects of the method of dose administration on parameter values when given using the intended scheme. Any potential effect of weight on parameter values will be accounted for by the study design itself by the balanced proportion of lower weight/higher weight participants receiving their dose using each of MP and Syringe driver.

The geometric least square mean (GLSM), GLSM differences and the corresponding 90% CI for the differences (MP [Test] - syringe driver [Reference]) will be calculated for PK parameters (log-transformed C_{max} , AUC_{0-t}). Back-transformed (anti-log) estimates of (GLSM, geometric least square mean ratio (GLSMR) and its 90% CI for the comparisons will be presented. In order to verify the normality assumption of the ANOVA, normal quantile-quantile plots will be used to visually inspect the distribution of residuals, and the potential impact of any deviations will be discussed.

PD analyses

All PD summaries will be done using PD-PPS by treatment group described under [section 5.1.1.3](#). Total IgG (observed values, change from Baseline, and percentage change from Baseline) will be listed and summarized for the PD Per Protocol Set. The geometric mean Total IgG concentration with 95% CI will be displayed graphically.

Derived parameters for the Total IgG response curve (AUC, maximum decrease in total plasma IgG, and time to minimum plasma concentration) will be listed and summarized for the PD Per Protocol Set.

The comparability of the total dose adjusted IgG Baseline-corrected AUC (IgG)/D between MP and the syringe driver will be assessed within an ANCOVA model with Baseline IgG value fitted as a covariate. The least square mean (LSM), LSM differences and the corresponding 95% CI for

the differences will be presented for total IgG. The analysis may be conducted on the log scale if the data exhibits substantial non-normality. In this case, the reason for the log-transformation will be described.

The following contrasts will be presented:

- Rozanolixizumab via Syringe Driver vs Rozanoliximab via MP
- Placebo via Syringe Driver vs Placebo via MP
- Rozanolixizumab via Syringe Driver vs Placebo via Syringe Driver
- Rozanoliximab via MP vs Placebo via MP

Additionally, observed values and change from Baseline in serum IgG concentrations at each scheduled assessment during the In-Clinic and SFU Periods will be summarized descriptively.

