1.2 Study design

This Phase 1 study is a randomized, participant-blind, investigator-blind, placebo-controlled safety/tolerability, pharmacokinetic (PK), and pharmacodynamic (PD) evaluation of a [REDACTED] rozanolixizumab subcutaneous (SC) dose administered to healthy participants by either a programmed syringe driver or by manual push (MP) via self-administration. As rozanolixizumab has not been administered SC to humans by MP, this study represents a preliminary assessment of the MP method prior to recommendation of this administration technique in the clinical dosing of rozanolixizumab.

Participants are divided into 2 body weight categories: ≥ 35 to < 50 kg and ≥ 50 kg. Within the higher body weight category, 16 participants were to be randomly allocated to syringe driver or MP cohorts and, subsequently, to rozanolixizumab (6 participants total) or placebo (2 participants total) (Figure 1-1). Participants of lighter body weights between ≥ 35 to < 50 kg are being investigated to a) support the newly recommended rozanolixizumab dosing with a fixed dose of [REDACTED] in adults of ≥ 35 kg to 50kg (via syringe driver administration) and (b) to assess the MP method for a [REDACTED] dose) investigational medicinal product (IMP) volume.

Within the lower body weight category, the allocation to either syringe driver or MP was to be determined by order of recruitment rather than randomization. The first 8 participants were to be allocated to the syringe driver cohort and randomly allocated to receive either rozanolixizumab [REDACTED] (6 participants total) or placebo (2 participants total). The subsequent 8 participants were to be allocated to the MP cohort and randomly allocated to receive either rozanolixizumab [REDACTED] (6 participants total) or placebo (2 participants total).

The treatment groups were planned as follows:

- Cohort 1 (participants with a body weight of ≥ 35 kg to < 50 kg) was planned to have 6 participants receive rozanolixizumab [REDACTED] and 2 participants receive placebo via syringe driver at a [REDACTED].
- Cohort 2 (participants with a body weight of ≥ 35 kg to < 50 kg) was planned to have 6 participants receive rozanolixizumab [REDACTED] and 2 participants receive placebo via MP through self-administration at a [REDACTED].
- Cohort 3 (participants with a body weight of ≥ 50 kg) was planned to have 6 participants receive rozanolixizumab [REDACTED] and 2 participants receive placebo via syringe driver at a [REDACTED].

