5 STATISTICAL ANALYSES

5.1 General Considerations

This is a Phase 1 study to evaluate the safety and tolerability of a [REDACTED] SC dose of rozanolixizumab administered to healthy participants by MP vs syringe driver.

Statistical evaluation will be performed by UCB or designee with oversight by the Statistical Sciences and Innovation Department of UCB. All analyses will be performed using SAS[®] version 9.4 or later (SAS Institute, Cary, NC, USA).

Missing data will not be imputed. Outlier detection and statistical analysis of outliers will not be performed. Unless otherwise stated, Baseline will be the last non-missing data collected prior to the IMP administration ([refer Section 5.1.1.1.4](#)).

Continuous variables will be summarized by cohort and in each cohort by treatment groups rozanolixizumab [REDACTED] or placebo, and day (where applicable); with statistics including, the number of study participants, mean, standard deviation (SD), interquartile range, median, minimum, maximum, and 95% confidence interval (CI), if applicable. Categorical variables will be summarized by cohort, treatment group, and day (where applicable) with frequency counts and percentages. Coefficient of variation (CV) and geometric mean will be used for PK parameters.

In addition, the results will be summarized by administration method (manual push or syringe driver), and within administration method, by treatment group (rozanolixizumab, regardless of dose, or placebo).

When reporting relative frequencies or other percentage values, the following rules apply:

- For values where all participants fulfill certain criteria, the percentage value will be displayed as 100
- For values where the absolute frequency is zero, there will be no percentage displayed at all
- All other percentage displays will use 1 decimal place

-
- Percentages displayed based on continuous data (eg, percentage changes from Baseline) will be displayed to 1 decimal place eg, 100.0 and 0.0.
 - Unless otherwise stated, the percentages will be based on the number of participants in the respective analysis population and treatment group.

When reporting descriptive statistics, the following rules will apply in general:

- “n” will be an integer.
- Mean (arithmetic and geometric), 95% CI, SD, and median will use 1 additional decimal place compared to the original data.
- Coefficient of variance (CV [%]) will be presented with 1 decimal place.

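### The only planned manual push vs syringe driver estimates for PK and PD pool a randomised contrast with a non-randomised one; the randomised ≥50 kg contrast is neither estimated nor identified

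*SAP*

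**What the plan says.** For PK, SAP 5.4.1.2 analyses the logs of Cmax/D and AUC(0-t)/D (D is the dose) in a "model with method (MP vs syringe driver) as a main effect, with no additional covariates". The output is one MP/SD geometric least squares mean ratio (GLSMR) with a 90% CI per parameter. Protocol 9.4.2 has the same method-only model.

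For PD, "The comparability of the total dose adjusted IgG Baseline-corrected AUC (IgG)/D between MP and the syringe driver will be assessed within an ANCOVA model"; the only covariate named is Baseline IgG. One of the four listed contrasts is MP vs SD on rozanolixizumab, with a 95% CI. None is by weight category. SAP 5.8 plans no subgroup analyses and SAP 5.4.2 no supportive secondary analysis.

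The SAP gives its reasons. The PK model is meant to "reflect the intended dosing scheme of fixed dosing". Of the result it says: "This will thus allow us to draw conclusions about the presence or absence of effects of the method of dose administration on parameter values", with the qualification that dosing follows that scheme. On weight it says: "Any potential effect of weight on parameter values will be accounted for by the study design itself by the balanced proportion" of lighter and heavier participants under each method.

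Allocation is set out in Protocol 4.1 and SAP 1.2. At ≥50 kg, 16 participants are randomised to SD or MP. At 35 to <50 kg, the first 8 recruited go to SD and the next 8 to MP, and only active vs placebo is randomised.

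SAP 5.4.1.2 also plans descriptive PK statistics by method, dose and body weight. The PK labels in SAP 5.1.1.3, however, list only two groups: all SD and all MP.

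**The concern.** The pooled estimate averages two contrasts of different quality. Cohort 4 vs Cohort 3 is a randomised comparison of methods. Cohort 2 vs Cohort 1 is not, because method there is fixed by recruitment order and possibly by dose as well. The SAP's defence of the method-only model is that weight category is balanced across methods. That argument answers weight. It does not answer recruitment order or dose.

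Dividing by D is the plan's only handling of dose. It works only if exposure and IgG response are proportional to dose. If Cohort 2 received the second dose, half of the MP arm would also lie outside the fixed-dose scheme that the model is said to represent.

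At stake is how the MP/SD ratio is read. The SAP intends to draw conclusions on a method effect from the pooled figure, and the study is a preliminary step before MP is recommended in clinical dosing (Protocol 4.1). The one contrast that isolates method by randomisation is not singled out anywhere.

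**Working it through.** **Design counts.** No power, margin or sample-size calculation is stated (SAP 2 and 3), so only the counts can be reproduced. Four cohorts of 8 give 32 randomised; four of 6 give 24 on rozanolixizumab, as in Protocol 7.2. Pooled, that is 12 MP vs 12 SD; at ≥50 kg it is 6 vs 6.

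**Share of the non-randomised contrast.** With 6 active participants in every cohort,

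ln(pooled ratio) = ½ ln(C4/C3) + ½ ln(C2/C1), so pooled ratio = √[(C4/C3) × (C2/C1)].

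If C4/C3 is 1.00, a dose-normalised C2/C1 of 0.80 gives √0.80 = 0.89, and 1.25 gives √1.25 = 1.12, whatever the cause. This step does not depend on the redacted doses.

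**Do dose and method differ together in Cohorts 1 and 2?** The dose values are redacted, so this is an inference.

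- For: Protocol 1.1 and 4.3 say that a further dose is assessed in low-weight participants. SAP 1.2 splits the low-weight aims, tying the fixed dose to one method and a separate dose or volume to the other: "50kg (via syringe driver administration) and (b) to assess the MP method for a" redacted quantity. Protocol 4.1 justifies the Cohort 1 sentinels by a dose not yet studied at that weight, and those in Cohorts 2 and 4 by infusion rate. SAP 5.1 summarises within method "by treatment group (rozanolixizumab, regardless of dose, or placebo").
- Against: the dose-level row of Protocol Table 6-1 is not visibly split by method, though it is partly redacted. Protocol 4.3 opens with a single planned dose.

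The first reading is better supported but cannot be confirmed.

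**Effect if the doses differ.** Let r be the dose ratio, Cohort 2 over Cohort 1, let exposure be proportional to dose^b, and assume no method effect. The dose-normalised C2/C1 is r^(b−1), and the pooled PK ratio is r^((b−1)/2). Neither r nor b is in the documents; both are assumptions.

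| r | b = 0.5 | b = 1 | b = 1.5 |
|---|---|---|---|
| 0.5 | 0.5^(−0.25) = 1.19 | 1.00 | 0.5^(0.25) = 0.84 |
| 0.8 | 0.8^(−0.25) = 1.06 | 1.00 | 0.8^(0.25) = 0.95 |
| 1 (equal doses) | 1.00 | 1.00 | 1.00 |

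For r above 1 the direction reverses. The C4/C3 ratio stays at 1.00 throughout.

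For PD on the untransformed scale, the pooled difference shifts by (r^(b−1) − 1)/2 of the Cohort 1 per-dose mean, where b now describes the IgG response. At r = 0.5 that is (1.414 − 1)/2 = +21% for b = 0.5 and (0.707 − 1)/2 = −15% for b = 1.5.

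**What the documents say on proportionality.** Protocol 2.2 reports that in the first-in-human study one SC dose gave no detectable concentrations, another gave them in only 2 participants, and exposure could be calculated at one dose only. This does not establish proportionality. It does not disprove it either, since assay limits contribute.

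**Precision of the split.** The 90% CI is the ratio multiplied and divided by exp[t(0.95, df) × s × √(2/n)], with s = √ln(1 + CV²). The CV is assumed.

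| CV | Pooled, n = 12, df 22 | ≥50 kg, n = 6, interaction model, df 20 | ≥50 kg alone, n = 6, df 10 |
|---|---|---|---|
| 30% | 1.23 | 1.34 | 1.36 |
| 50% | 1.39 | 1.60 | 1.64 |

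For PD in active participants, the 95% half-width in residual SDs is t(0.975, df) × √(2/n): 0.85 pooled (df 21) and 1.21 split (df 19).

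The interaction ratio has a 90% CI factor of exp[t(0.95, 20) × s × √(4/6)] = 1.51 at 30% CV and 1.95 at 50%. It is too imprecise to justify pooling by its apparent absence.

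**The case against.** The strongest reply has four parts.

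First, the dose difference cannot be verified, and if Cohorts 1 and 2 share a dose every dose figure above is nil. That stands, and the dose part is therefore conditional. The non-randomised allocation is stated openly and does not depend on dose. Its size is unknown, however, and the documents offer no mechanism for drift in assay-measured outcomes at a single centre.

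Second, the plan is reasoned: parameters are dose-adjusted, and a contrast over all weights is a legitimate target. That also stands, and it is why the pooled estimate should be kept. What is missing is any check of proportionality and any argument on dose or recruitment order.

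Third, a reader might infer that the plan leaves no way to see the ≥50 kg comparison. The documents do not support that. The number of observations, geometric mean and geometric CV by method, dose and weight give a crude C4/C3 ratio and a two-sample CI. This is exact for undivided Cmax and AUC, and approximate after division by D if actual doses vary. For PD, SAP 5.1.1.3 provides by-cohort summaries. But no such contrast is planned as an estimate or identified as the randomised one, and the baseline-adjusted PD contrast cannot be recovered from summaries.

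Fourth, the split is imprecise and the comparison is exploratory, with no hypothesis test (SAP 2). Both are true. They limit the severity, and they do not make the pooled figure a cleaner measure of method.

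**Conclusion.** The point holds as a matter of interpretation. Half of each pooled MP vs SD estimate comes from a contrast in which method was not randomised, assuming 6 evaluable active participants per cohort. If the doses in Cohorts 1 and 2 differ, as the text suggests, any departure from dose proportionality enters as well. At an assumed r = 0.5 it moves a true PK ratio of 1.00 to 1.19 or 0.84.

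Two stronger readings are not supported. A reader might infer that the pooled ratio is known to be biased; with the doses redacted, neither size nor sign can be determined, and the dose component is zero under proportionality or equal doses. A reader might also infer that pooling would hide a real loss of exposure under MP. At r = 0.5 and b = 0.5 a true 0.80 would read 0.80 × 1.189 = 0.95, but at b = 1.5 it would read 0.80 × 0.841 = 0.67. The sparse SC data in Protocol 2.2 do not favour the first case.

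The primary endpoint, incidence of TEAEs, is reported by cohort and is unaffected. Severity is minor to moderate.

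**What to change.** Keep the pooled contrast and add to SAP 5.4.1.2:

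> The logs of Cmax/D and AUC(0-t)/D will also be fitted with method, weight category and their interaction. The MP/SD GLSMR with 90% CI for the ≥50 kg category (Cohort 4 vs Cohort 3) will be presented beside the pooled GLSMR and labelled as the randomised method contrast. It will be presented whatever the interaction estimate shows.

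Add the same split, with 95% CI, to the PD ANCOVA, restricted to rozanolixizumab-treated participants. AUC(IgG)/D is undefined for placebo because D is zero; the placebo contrasts listed in SAP 5.4.1.2 need attention for the same reason.

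Footnote the low-weight and pooled results as not isolating method from recruitment order and, if doses differ, from dose. Reconcile the two PK labels in SAP 5.1.1.3 with the summaries by method, dose and body weight in SAP 5.4.1.2, so that the cohort-level PK statistics are certain to be produced.

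The cost is one extra model per parameter, some footnotes and an SAP amendment before database lock; no new data are needed. The added interval is wider (90% CI factor 1.34 to 1.36 against 1.23 at an assumed 30% CV), which is the precision that the randomised part of the design supports.

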## 4 STUDY DESIGN

### 4.1 Overall design

This Phase 1 study is a randomized, participant-blind, investigator-blind, placebo-controlled safety/tolerability, PK, and PD evaluation of a [REDACTED] rozanolixizumab SC dose administered to healthy participants by either a programmed syringe driver or by MP via self-administration. As rozanolixizumab has not been administered SC to humans by MP, this study represents a preliminary assessment of the MP method prior to recommendation of this administration technique in the clinical dosing of rozanolixizumab.

Participants will be divided into 2 body weight categories:  $\geq 35$  to  $< 50$ kg and  $\geq 50$ kg. Within the higher body weight category, 16 participants will be randomly allocated to syringe driver or MP cohorts and, subsequently, to rozanolixizumab (6 participants total) or placebo (2 participants total) (Figure 1-1). Participants of lighter body weights between  $\geq 35$  to  $< 50$ kg are being investigated to a) support the newly recommended rozanolixizumab dosing with a fixed dose of [REDACTED] in adults of  $\geq 35$ kg to 50kg (via syringe driver administration) and (b) to assess the MP method for a [REDACTED] IMP volume.

Within the lower body weight category, the allocation to either syringe driver or MP will be determined by order of recruitment rather than randomization. The first 8 participants will be allocated to the syringe driver cohort and randomly allocated to receive either rozanolixizumab [REDACTED] (6 participants total) or placebo (2 participants total). The subsequent 8 participants will be allocated to the MP cohort and randomly allocated to receive either rozanolixizumab [REDACTED] (6 participants total) or placebo (2 participants total).

The treatment groups are planned to be as follows:

- Cohort 1 (participants with a body weight of  $\geq 35$ kg to  $< 50$ kg) is planned to have 6 participants receive rozanolixizumab [REDACTED] and 2 participants receive placebo via syringe driver at a [REDACTED].
- Cohort 2 (participants with a body weight of  $\geq 35$ kg to  $< 50$ kg) is planned to have 6 participants receive rozanolixizumab [REDACTED] and 2 participants receive placebo via MP through self-administration at a [REDACTED].
- Cohort 3 (participants with a body weight of  $\geq 50$ kg) is planned to have 6 participants receive rozanolixizumab [REDACTED] and 2 participants receive placebo via syringe driver at a [REDACTED].

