## 7.2 Participant discontinuation/withdrawal from the study

Participants are free to withdraw from the study at any time, without prejudice to their continued care. The study is designed to collect data on 24 participants that receive rozanolixizumab (6 per cohort). If study participants discontinue before the end of the safety evaluation period, replacement participants may be considered at the discretion of the sponsor, depending on how the discontinuation affects the study's ability to collect sufficient data to support the study

objectives. For each case of participant discontinuation, the decision on whether to recruit a replacement and the reason behind the decision will be documented.

If the participant withdraws consent for disclosure of future information, the sponsor may retain and continue to use any data collected before such a withdrawal of consent.

If a participant withdraws from the study, he/she may request destruction of any samples taken and not tested, and the investigator must document this in the site study records. Participants who withdraw from the study will be encouraged to return to the clinic to complete the Withdrawal Visit (see [Table 1-1](#)).

See [Table 1-1](#) for data to be collected at the time of study discontinuation and follow-up and for any further evaluations that need to be completed.

Participants should be withdrawn from the study if any of the following events occur:

1. Participant develops an illness that would interfere with his/her continued participation.
2. Participant is noncompliant with the study procedures or medications in the opinion of the investigator.
3. Participant takes prohibited concomitant medications as defined in this protocol that might interfere with the outcome of the study or might be an increased risk to the study participant.
4. Participant withdraws his/her consent.
5. There is confirmation of a pregnancy during the study, as evidenced by a positive pregnancy test.
6. The sponsor or a regulatory agency requests withdrawal of the participant.

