2 STATISTICAL HYPOTHESES

Not applicable, there is no hypothesis testing in the study.

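### The SAP promises conclusions about the absence of a method effect on PK, but nothing in the plan defines which result would show absence

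*SAP*

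**What the plan says.** SAP Section 5.4.1.2 compares log-transformed, dose-adjusted Cmax and AUC(0-t) between manual push (MP) and syringe driver in an ANOVA "model with method (MP vs syringe driver) as a main effect, with no additional covariates". It explains that this structure mirrors the intended fixed-dose scheme, and then states: "This will thus allow us to draw conclusions about the presence or absence of effects of the method of dose administration on parameter values", with the qualification that this is under the intended scheme. Weight is left out because of the "balanced proportion of lower weight/higher weight participants receiving their dose using each of MP and Syringe driver".

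The planned output is a geometric least squares mean ratio, MP over syringe driver, and "its 90% CI for the comparisons will be presented". On hypotheses, SAP Section 2 says: "Not applicable, there is no hypothesis testing in the study". SAP Section 3 reports no formal sample size calculation and calls the number of participants sufficient for the primary objective, which is safety and tolerability. The objectives tables (Protocol Section 3, SAP Section 1.1) list the PK comparison as exploratory.

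**The concern.** The sentence claims two kinds of inference. Presence of an effect has a natural reading: a CI that excludes 1. Absence does not. To conclude that method makes no relevant difference, one must first say how large a difference would matter and then show that the CI rules it out. The plan supplies no such limit.

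Protocol Section 4.1 describes the study as a preliminary assessment made before MP is recommended for clinical dosing. A report author could cite the SAP as prespecified support for a statement that method does not affect exposure. Such a statement would rest on an inference that the plan does not define.

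**Working it through.** **1. Is there a criterion for absence?** SAP Section 5.4.1.2 gives a model, a ratio and a CI, but no limits. SAP Section 2 has no hypotheses. SAP Section 3 and Protocol Section 9.8 have no power, alpha, SD or margin. Neither document contains a decision rule for this comparison. This step needs no assumed figure.

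**2. Numbers per method.** The plan's total reproduces: 4 cohorts × 8 = 32. Protocol Section 7.2 says the study is "designed to collect data on 24 participants that receive rozanolixizumab (6 per cohort"), and 4 × 6 = 24. MP is used in Cohorts 2 and 4 and the syringe driver in Cohorts 1 and 3, so the comparison is 6 + 6 = 12 against 12. That split is derived, not printed. Residual df = 24 − 2 = 22.

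**3. Width of the 90% CI.** No between-participant CV is given, so 20% to 60% is an assumed range.
- SD on the log scale: s = √ln(1 + CV²).
- Half-width on the log scale: t(0.95, 22) × s × √(2/12) = 1.717 × 0.408 × s = 0.701 × s.
- Example at CV 30%: s = √ln(1.09) = 0.294; half-width = 0.701 × 0.294 = 0.206; limits exp(∓0.206) = 0.81 and 1.23.

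**4. How often would the CI contain 1 if the true ratio were 1.25?** The t statistic follows a noncentral t with 22 df and noncentrality ln(1.25) / (0.408 × s). The CI contains 1 when |t| < 1.717. At CV 30% the noncentrality is 0.223 / (0.408 × 0.294) = 1.86, and the probability is 44%.

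**5. How often would the CI fall inside limits if the true ratio were 1?** Neither pair of limits below is in the documents; both are assumptions used only for illustration. The probability is that of two one-sided 5% tests for two parallel groups, integrated over the chi-square distribution of the variance estimate with 22 df.

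| Assumed CV | s | 90% CI at observed ratio 1 | CI contains 1 when true ratio is 1.25 | CI within 0.80-1.25 when true ratio is 1 | CI within 0.67-1.50 when true ratio is 1 |
|---|---|---|---|---|---|
| 20% | 0.198 | 0.87-1.15 | 15% | 70% | >99% |
| 30% | 0.294 | 0.81-1.23 | 44% | 16% | 90% |
| 40% | 0.385 | 0.76-1.31 | 60% | 1.3% | 61% |
| 60% | 0.555 | 0.68-1.48 | 75% | about 0% | 12% |

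**6. Reading the table.** A CI containing 1 is weak evidence against a 25% difference unless the CV is near 20%. Whether the CI would fall within limits depends heavily on both the CV and the limits, and the plan fixes neither.

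**7. A limit on interpretation outside the CI.** In the lower weight category, "the allocation to either syringe driver or MP will be determined by order of recruitment rather than randomization" (Protocol Section 4.1). For 6 of the 12 in each group, therefore, method is tied to time of entry, and the CI does not reflect any bias from that. Balance by weight category guards against confounding by weight category. It does not remove weight-related variation from the residual, so any such variation widens the CI.

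**The case against.** The strongest reply is that the sentence explains a choice of model rather than setting a rule. Read with its qualifier, it says that the method effect is to be estimated across weights because fixed dosing ignores weight. The planned output is estimation: a reader sees the ratio and its 90% CI and can judge it against any limit. The comparison is labelled exploratory, hypothesis testing is disclaimed and the study is called preliminary. Most of this stands. The analysis is sound and needs no change. It does not remove the point, because the sentence still tells the report author that absence may be concluded and no other text restricts that. The SAP also describes the analysis under Section 5.4.1, headed as key or confirmatory secondary endpoints, although the objectives tables list the comparison as exploratory.

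Three stronger readings are tempting but unsupported:
- A reader might infer that the SAP will declare no effect whenever the CI includes 1. No text says that the CI will be compared with 1.
- A reader might infer that 12 against 12 is simply too few to support absence. That depends on a CV and a margin that the documents do not give. At CV 20% the chance of meeting 0.80-1.25 is 70%, and with 0.67-1.50 it is 90% at CV 30%.
- A reader might infer that the sample size is deficient. It was justified only for the safety objective, so it cannot be faulted for missing a PK equivalence target that it never had.

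**Conclusion.** The point holds in a limited form. The plan states that the ANOVA can support conclusions about absence of a method effect, but with no margin or decision rule, absence is undefined and unsupported. That conclusion rests on the text alone.

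The size of the problem rests on assumed CVs and on the full planned 12 per method. From CV 20% to 60%, the 90% CI at an observed ratio of 1 widens from 0.87-1.15 to 0.68-1.48, and a true 25% higher exposure leaves 1 inside the CI in about 15% to 75% of trials. This is an overstated interpretation of an exploratory comparison, not a wrong analysis.

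**What to change.** In SAP Section 5.4.1.2, replace the sentence on presence or absence with:

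*The geometric mean ratio (MP/syringe driver) and its 90% CI estimate the method effect under the intended dosing scheme; this comparison is exploratory, no equivalence margin is set, and a CI containing 1 will not be read as absence of an effect.*

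If the sponsor does want to conclude absence, the alternative is to prespecify and justify limits, report the CI against them, and acknowledge the precision available at 12 per method.

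The wording change alters no model, analysis set, table or participant number. Its only cost is a less favourable stated claim. Adding expected CI widths to SAP Section 3 would be optional, since that section addresses the safety objective.
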